All prisoners in the study undergo an oral examination to establish a baseline (hereafter T0) of oral health and a comprehensive questionnaire to identify risk factors and their attitude towards their oral health and oral treatment. Norwegian speaking prisoners are then randomized into either a treatment or control group. In the treatment group, dental staff initiate a conversation with the prisoner based on techniques from MI. Both groups finally receive a toilet bag with basic equipment to regularly clean their teeth. After 4 weeks and 12 weeks (hereafter T1 and T2), prisoners are invited back for another oral examination and a follow-up questionnaire, to measure changes in oral hygiene, oral cleaning routines, and attitude towards their oral health. At T1 we also conduct a screening of general learning difficulties using the validated screening tool HASI (Hayes, 2002). If the intervention proves to be an effective tool in improving oral hygiene, oral cleaning routines, and/or attitude towards own oral health, it can serve as an alternative proactive approach to improve oral health of a vulnerable group in society. If the improvements in oral hygiene and oral cleaning routines are long lasting, this may in turn lead to a reduced need of oral treatment. An improved attitude towards own oral health may, together with other rehabilitation programs in prison, improve the prisoner's self-esteem and chances to successfully returning to society after having served their prison sentence.

Study Design

Hypothesis:

H1: The conversation based on Motivating Interviewing (hereby the intervention) leads to a reduction in observed plaque and gingival inflammation for prisoners.

H2: The intervention leads to improved reported cleaning routines of prisoners in general, and particularly brushing of teeth.

H3: The intervention leads to a reduction in prisoners' intake of food and drinks in total, and particularly in-between meals.

H4: The intervention leads to improved perceptions about the prisoner's oral health. It improves how they view their oral health, they consider their oral health as more important, they report an increased wish to improve it, and they have increased efforts to improve it.

H5: The intervention leads to an increase in number of questions the prisoner asks during their visit with the dental staff, suggesting an increase in curiosity concerning their oral health.

Treatment effects and measurements:

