Prisoners are not informed whether they are in the treatment or control group and are therefore blind to treatment status. Dental staff are blind to prisoners' treatment status at the time of the first oral examination and questionnaire. The prisoner's treatment status is revealed just after this. Hence, dental staff collects all data prior to knowing the prisoner's treatment status, and only learn this when they start the MI-based conversation. When prisoners are back at T1 and T2 for follow-up oral examinations and questionnaires, dental staff might still remember whether the prisoner was treated or not. To partially account for potential bias in the oral examination (assessment of oral hygiene and inflammation in gingival), there are two independent assessments of this at T1 and T2. See pre-specification of analytical decisions for more on this.

Power calculations:

We have used GPower and Optimal Design to conduct power calculations.

GPower is used to calculate required sample size for simple comparison of means for the main variables of interest between the treatment and control group, without considering that data is collected at multiple sites. We choose the non-parametric Wilcoxon-Mann-Whitney test, set alpha to 0.05 and required power to 0.8. There is uncertainty concerning the effect size. Previous literature offers some guidance, however there are several important differences to our study. MI-interventions to change oral health have previously been tested on periodontist patients and patients with mental illness, populations that differ from ours. For our main variable of interest, level of plaque, these studies have found effect sizes ranging from 0.286 to 1.213¹. However, one should note that these studies have used different indexes to measure plaque, questioning the comparability of the effect sizes. Setting the power estimate to a moderate level in this range, to 0.5,

¹ An effect size of 0.286 was found after 12 weeks in Brand et al. (2012), whereas an effect size of 1.213 was found in Godard et al. (2011).

our required sample size is 106 prisoners. If we use a more conservative estimate and set it to the lowest effect size observed in the studies referred to above (0.286), the required sample size is 320.

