Optimal Design is used to calculate the Minimum Detectable Effect Size (MDES) given that we block on prison level. Here we choose the Multi-Site trials under Person Randomized Trials. We set alpha to 0.05 and required power to 0.8. As we block on prison, we set number of sites (J) to 4. There are great uncertainty concerning effect size variation, how much of the variation in the outcome that can be explained by the blocking variable, and how much of the variation in the outcome can be explained by the covariate variable. Thus, we present power calculations based on bounds of these values. We set the range of effect size variation from 0.0 (equivalent to the fixed-effects model) to 0.05. Furthermore, we assume that the blocking variable can explain 20% to 30% of the variation in the outcome. And finally, we use the pre-intervention MPS index score from the oral examination as a covariate, expected to explain 50% to 60% of the variation in the post-intervention MPS index score.

Given these boundaries, and assuming we can recruit 100 prisoners in each prison, the most optimistic scenario allows us to detect an effect size of about 0.15. On the other hand, should we end up in the other end of the boundaries, we are only able to detect an effect size of about 0.55. The calculation is very sensitive to changes in the effect size variation, and less sensitive to changes in how much variation the blocking variable and the covariate variable can explain. The number of prisoners recruited in each prison is also an uncertain number. The prisons differ in size and number of prisoners. We are likely to have more than 100 prisoners recruited in three out of four prisons. The smallest prison in the region has only 18 rooms. The calculations above have not considered the imbalance of prison size.

Pre-specification of analytical decisions

Statistical model specification:

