To test the overall effects of the intervention on our primary and secondary outcome variables, we will conduct non-parametric Wilcoxon Mann-Whitney U-tests. Given the ordinal outcome variables, we consider this test as more appropriate alternative relative to traditional two independent sample t-tests. We will compare the means of the treatment group and the control group at T0, T1 and T2. At T0 we expect no differences in means as no intervention has occurred. At T1 and T2 we expect better scores for the treatment group relative to the control group. Notably, our primary interest will be the difference in means at T1, as we expect more missing data at T2 due to prisoners being released from prison. However, for the intervention to have a long-lasting improvement on the prisoner's oral health, it is important that the intervention successfully enables the prisoner to make lasting changes. If we do not find a statistical difference between the treatment and the control group at T2, however, it may be hard to tell whether this is due to the intervention effect fading out or lack of power. See power analysis for more details on this, in which we show effect sizes possible to detect at different number of observations, given that power is set to 0.8 and number of sites is set to 4. As drop-out increases at T2, the higher the effect size must be for us to be able to detect any statistical difference between the groups.

Moreover, we are going to run multiple ordinal logistic regressions where we include selected covariates (see below). Running regressions allow us to control for the baseline measures of plaque

by using the baseline score of the outcome variables as a lagged dependent variable, in addition to including other covariates likely to correlate with the treatment and to explain variation in the dependent variable. For robustness purposes we also run regressions with fixed effects, controlling for unobserved individual time-invariant characteristics.

Covariates:

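### The required sample sizes of 106 and 320 are one-tailed results, but no one-sided test is declared; tested two-sided at 0.05 they give about 70% power, not 80%

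*Combined protocol and SAP*

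**What the plan says.** The Power calculations section describes the GPower step: "We choose the non-parametric Wilcoxon-Mann-Whitney test, set alpha to 0.05 and required power to 0.8". It is a plain two-group comparison, done "without considering that data is collected at multiple sites". Two results are given. At an effect size of 0.5, "our required sample size is 106 prisoners". At 0.286, the lowest effect in the cited literature, "the required sample size is 320". Neither the number of tails nor the parent distribution is stated.

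The same section then reports detectable effects from Optimal Design at the same alpha and power with four sites, "assuming we can recruit 100 prisoners in each prison". These run from about 0.15 at best to the worst case, where "we are only able to detect an effect size of about 0.55". Tails are again not stated.

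The analysis test under Statistical model specification is the Mann-Whitney U-test, with T1 as the time point of primary interest. No sidedness is given there either. The direction of the expected effect is clear. H1 under Hypothesis says the intervention "leads to a reduction in observed plaque and gingival inflammation for prisoners", and the model section adds: "At T1 and T2 we expect better scores for the treatment group relative to the control group".

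**The concern.** Sample sizes of 106 and 320 are small for two-sided tests of these effects at 80% power. If they came from a one-tailed calculation but the T1 test is run two-sided, the stated power is not delivered. A reader who compares the number analysed at T1 with 320 would then take the conservative case to be powered at 80% when it is not.

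There is also a pre-specification gap. The Conclusion presents the document as recording analytical decisions made before any analysis, and sidedness is one that it leaves open. When the effect lies in the expected direction, a one-sided p-value from this test is about half the two-sided one, so the choice should not be available after the data are seen.

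**Working it through.** **Inputs.** From Power calculations: alpha 0.05, power 0.80, standardised effects d = 0.5 and d = 0.286. From Randomization: balanced blocks of four, hence 1:1 allocation. Assumed, because not stated: the parent distribution and the number of tails.

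**Method.** In the asymptotic-relative-efficiency (A.R.E.) method for this test, the total N is multiplied by the A.R.E. and a noncentral t is used:

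- df = N × A.R.E. − 2
- noncentrality = d × √(N × A.R.E. / 4)
- normal parent: A.R.E. = 3/π = 0.955

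**Reproducing the plan's figures (one-tailed, normal parent).**

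- d = 0.5, N = 106: df = 99.2, noncentrality = 0.5 × √(101.22/4) = 2.515, critical t = 1.660, power 80.3%. The next smaller even total, 104, gives 79.65%. Required N = 106, an exact match.
- d = 0.286, N = 320: df = 303.6, noncentrality = 0.286 × √(305.58/4) = 2.500, critical t = 1.650, power 80.2%. A total of 318 gives 79.996%, just short. Required N = 320, an exact match. (If df is taken from the unscaled N, 318 just qualifies; 106 is unchanged.)

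**Other settings tried (total N for d = 0.5 and d = 0.286).**

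| Parent | One-tailed | Two-tailed |
|---|---|---|
| Normal (3/π) | **106, 320** | 134, 404 |
| Uniform / t-test (1.0) | 102, 304 | 128, 386 |
| Logistic (π²/9) | 92, 278 | 118, 352 |
| Laplace (1.5) | 68, 204 | 86, 258 |
| Minimum A.R.E. (0.864) | 118, 352 | 148, 448 |

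Only the one-tailed normal setting gives the pair. A two-sided test at alpha 0.10 is equivalent, but the stated alpha is 0.05.

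**Two-sided at 0.05, normal parent.**

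- Power at N = 106, d = 0.5 (critical t = 1.984): 70.2%.
- Power at N = 320, d = 0.286 (critical t = 1.968): 70.3%.
- Required N: 134 (80.1%) and 404 (80.0%). 134/106 = 1.264 and 404/320 = 1.2625, both about 26% more.
- Effect detectable at 80% power: 0.56 with 106 and 0.32 with 320.
- With 400 analysed (4 × 100, no loss): 79.6% at d = 0.286, against 87.4% one-sided, and 99.8% at d = 0.5. With 500 analysed: 87.7% at d = 0.286.

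**Checks by simulation.** With normal data (20,000 trials), two-sided power at 106 and 320 is 70.7% and 70.3%; one-sided it is 80.8% and 80.1%. MPS is a discrete sum from 2 to 8, so a second check used two four-point items cut from a bivariate normal. The correlation (0.4 or 0.6) and two sets of cut points were assumed, and d was fixed on the observed sum (40,000 trials per case). At 106 and 320, power was 70.3–71.6% two-sided and 80.5–81.1% one-sided. At 134 and 404, it was 80.3–81.1% two-sided.

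**The four-site bounds.** The Optimal Design settings are not shown, so this step is inference. Take standard error = √[(effect-size variance + 4 × residual variance / n) / J], with J = 4, n = 100, and residual variance = (1 − share explained by blocking) × (1 − share explained by the covariate).

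- Worst case (0.05; 20%; 50%): √[(0.05 + 4 × 0.40/100)/4] = 0.1285. On 3 df the detectable effect is 0.547 two-sided and 0.424 one-sided.
- Best case (0; 30%; 60%): √[(4 × 0.28/100)/4] = 0.0529. The detectable effect is 0.149 two-sided and 0.132 one-sided.

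The two-sided version matches both stated bounds, about 0.55 and about 0.15. Other ways of combining blocking and covariate give 0.53–0.56 two-sided and 0.41–0.44 one-sided at the upper end. At the lower end they range from 0.089 to 0.178 two-sided and from 0.079 to 0.158 one-sided, so that end does not discriminate.

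**The case against.** The strongest reply is that nothing has been miscalculated. Both figures are right under one consistent setting, and one-tailed sizing suits directional hypotheses. The drop to 70% occurs only if the T1 test is run two-sided, which the plan does not say. No decision depends on 106 or 320: the aim of about 500 comes from capacity (Expected timeline), and the model section's pointer to the power analysis concerns the four-site calculation. The plan also admits that its effect sizes are uncertain, and the choice between 0.5 and 0.286 moves N about threefold, against 26% for sidedness.

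Much of this stands. A one-sided test may have been intended, the shortfall is conditional, and the practical reach is limited. The four-site comparison is only supporting evidence.

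It does not remove the problem. An expected direction is not a rejection rule, and alpha 0.05 without tails will ordinarily be read and run as two-sided. Nor does the aim of 500 settle the matter. Prisoners without sufficient Norwegian are not randomised, and attrition is expected to be fairly high with no rate given. A T1 analysis of between 320 and 404 is therefore possible. In that range the plan's own benchmark calls the conservative case powered, while a two-sided test falls short.

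**Conclusion.** The concern holds. The stated sizes are one-tailed results presented without tails, and no one-sided test is declared anywhere. If the primary T1 test is two-sided at 0.05, power at 106 and 320 is about 70% rather than 80%, and the matching requirements are 134 and 404 analysed.

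This rests on the normal parent, the only one tried that reproduces the plan's numbers. Across the other parents tried, two-sided power at the stated sizes runs from 66% to 88%. The figures are for the unadjusted Mann-Whitney test; regressions adjusting for baseline are also planned but are not named as the primary test. At d = 0.5 the planned numbers are ample either way, so the practical consequence is confined to d = 0.286. This should be fixed before analysis, but it does not threaten the design.

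**What to change.** State the sidedness once and put the power section on the same basis.

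- **Two-sided.** Under Statistical model specification, add: *The primary Mann-Whitney test of MPS at T1 is two-sided at alpha 0.05.* Under Power calculations, restate: *Assuming a normal parent distribution (A.R.E. 3/π) and a two-sided test at alpha 0.05, 134 (d = 0.5) or 404 (d = 0.286) prisoners analysed at T1 give 80% power.*
- **One-sided.** Declare and justify a one-sided test before any analysis, keep 106 and 320, and put the four-site bounds on the same basis.

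The cost is about two sentences, with no extra recruitment or change of design. The two-sided route leaves a less favourable statement: at d = 0.286, 400 analysed gives about 80% power only if no one is lost. The one-sided route gives up a formal test for worsening.

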There are four prisons in Rogaland County, all of which are included in the study. Three prisons are categorized as high security prisons, and one is categorized as a low security prison. The main difference between high and low security prisons are the level of security measures, as prisoners in the low security prisons are allowed to move more freely within the prison. The low security prison is mainly used for less serious criminal offences, with a sentence time of between six months and two years. Those convicted to less than six months can apply to serve the time with an ankle bracelet, whereas those convicted for more than two years start serving in a high security prison. However, many high security prisoners are transferred to low security prison to serve the final part of their sentence. Hence, the population across prisons are likely to vary due to the severity of the criminal offence they have committed, especially across high and low security prisons. However, as those with the least serious criminal offences serve time with an ankle bracelet, and those with more severe convictions often serve the final part of their sentence in a low security prison, the populations may not be that different from each other.

The prison population may also contain prisoners who normally live outside of Rogaland County. If there is available capacity in the prisons in Rogaland County, and other parts of Norway have queues of people waiting to serve their sentence, they could end up serving their time in a prison in Rogaland County. Hence, the prisoners do not necessarily originate from or live in Rogaland County to serve their prison sentence in Rogaland County.

Recruitment is done somewhat differently across prisons, and different for those already imprisoned at the time of the start of data collection and those arriving in the prison during the data collection period. For those already imprisoned at the start of data collection, they are either informed about the study by prison officers or dental staff. We wanted this process to be done exclusively by prison officers, but capacity constraints forced us to use our own staff in two of the prisons. The information given is the same across all prisons, based on an information letter, which is also distributed to the prisoners. They then give their preliminary consent to participate within a couple of days after being informed.

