The main covariate included in the analysis is the pre-intervention MPS index score. For our secondary outcome variables, the equivalent pre-treatment observation is used as covariate to control for pre-intervention status. We include these as they are likely to explain a lot of the variation in the outcome variable. Furthermore, we include a dummy variable for each prison, to control for prison-specific variation, and a dummy variable for the person who completed the MI-intervention with the prisoner.

As described below, we will also conduct heterogeneous analysis. Covariates that are relevant for such analysis (HASI and depressive symptoms) will also be included in the overall analysis.

Other covariates may be included, however given that we have successfully randomized prisoners, they should not affect our results. For robustness purposes, we will run analysis that include individual-specific covariates such as age, education, and length of prison sentence.

Heterogeneous analysis:

We will study heterogeneous effects of the intervention depending on their baseline score of the primary outcome variable. Those who score high on level of plaque have the greatest improvement potential. However, they might also be those with the least interest in taking care of their oral health. As motivational interviewing is designed to also motivate those who are not motivated, they may still experience the greatest improvement from the intervention.

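### The stated detectable-effect range of about 0.15 to 0.55 mixes a fixed-prison and a random-prison model, and no planned test uses the model behind 0.55

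*Combined protocol and SAP*

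**What the plan says.** The second half of Power calculations uses Optimal Design: "Here we choose the Multi-Site trials under Person Randomized Trials". The settings are "We set alpha to 0.05 and required power to 0.8" and "As we block on prison, we set number of sites (J) to 4". The key input is how much the treatment effect varies between prisons: "We set the range of effect size variation from 0.0 (equivalent to the fixed-effects model) to 0.05". Blocking is assumed to explain 20% to 30% of outcome variance, and the baseline mucosal-plaque score 50% to 60%. With 100 prisoners per prison, the favourable end is about 0.15; at the other end, "we are only able to detect an effect size of about 0.55".

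Statistical model specification plans unadjusted Wilcoxon-Mann-Whitney tests for the overall effect, then ordinal logistic regressions with the baseline score, and regressions with individual fixed effects for robustness. Under Covariates, "we include a dummy variable for each prison, to control for prison-specific variation". Research population states: "There are four prisons in Rogaland County, all of which are included in the study".

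Statistical model specification also warns that a null result at T2 could mean either fading or lack of power. For that question it refers the reader to the four-site power calculation.

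**The concern.** A detectable effect is useful only if it belongs to the test that will be run. Effect size variation of 0.05 treats the four prisons as a sample from a wider set of prisons, with the average effect tested against between-prison variation. No section plans a random prison effect, a random treatment-by-prison effect or a test on 3 degrees of freedom. By the plan's own label, variation of 0.0 is the fixed-effects case, and that is the case a prison-dummy regression corresponds to.

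What is at stake is how a null result is read. The 0.55 is governed by the number of prisons and hardly at all by the number of prisoners, so it cannot show how drop-out by T2 erodes sensitivity. It also says nothing about the Mann-Whitney test, which the plan names first.

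**Working it through.** **Inputs** (Power calculations unless noted): J = 4 prisons; n = 100 per prison; effect size variation s² = 0 to 0.05; share explained by blocking B = 0.2 to 0.3; share explained by baseline R² = 0.5 to 0.6; alpha 0.05; power 0.8; 1:1 allocation (Randomization). Sidedness is not stated; two-sided is taken. R² is applied to the variance left after blocking, a reading that recovers both published figures.

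**Reproducing 0.55 (random prison effects).** Variance of the average effect = [s² + 4(1−B)(1−R²)/n]/J, with a noncentral F test on (1, 3) df.
- At s² = 0.05, B = 0.2, R² = 0.5: (0.05 + 0.016)/4 = 0.0165, so SE = 0.128.
- The detectable effect is 0.547, or 4.26 standard errors. This matches the plan.
- With the same variance but a large-sample multiplier (2.80), the result is only 0.36. The 3 df are needed to reach 0.55.
- With unlimited prisoners per prison: 4.26 × √(0.05/4) = 0.476. More prisoners hardly help.

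**Reproducing 0.15 (fixed prison effects).** Variance = 4(1−B)(1−R²)/400, on (1, 392) df.
- At B = 0.3, R² = 0.6: 0.0028, SE = 0.0529, detectable effect 0.149. This matches the plan.
- The random model on 3 df with s² = 0 would give 0.225, so the two published ends do not come from one model.

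**Steps between the models at the pessimistic B = 0.2, R² = 0.5:** fixed effects 0.178; moving to 3 df with s² = 0, 0.269; adding s² = 0.05, 0.547.

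**Values for the planned tests** (two-sided 0.05, power 0.8). Regression: 2.80 × √[4(1−B)(1−R²)/N]. Mann-Whitney: 2.80 × √[4/(0.955N)], where 0.955 is its efficiency for normal data.

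| N analysed | Prison dummies + baseline (linear) | Unadjusted Mann-Whitney |
|---|---|---|
| 400 | 0.15 to 0.18 | 0.29 |
| 320 (assumed) | 0.17 to 0.20 | 0.32 |
| 200 (assumed) | 0.21 to 0.25 | 0.41 |

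**Simulation check of the regression values at 400.** With a continuous outcome, power was 0.81 at d = 0.15 (B 0.3, R² 0.6) and 0.80 at d = 0.178 (B 0.2, R² 0.5). With the outcome cut into seven levels at assumed cut-points, still analysed by the linear dummy model, power fell to about 0.75. The detectable effect is therefore somewhat larger on the actual score.

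**Sidedness of the GPower figures.** With the same efficiency, one-sided multiplier 2.49: N = 106 gives 0.494 and N = 320 gives 0.284, close to the plan's 0.5 and 0.286. Two-sided, they give 0.557 and 0.321. The 106 and 320 thus match a one-sided test, whereas 0.55 matches a two-sided one.

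**If wider inference is meant.** With s² = 0.05, B = 0.2 and R² = 0.5, the dummy model's SE is about 0.063 against 0.128 for prisons in general. Letting unmodelled heterogeneity enter the residual, the model's SE is √[4(0.4 + 0.0125)/400] = 0.0642. Then 1.96 × 0.0642/0.1285 = 0.98, and a nominal 5% test rejects about 33% of the time.

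**The case against.** **The plan is open about its bounds.** It labels variation 0.0 as the fixed-effects case, stresses uncertainty and says the result is very sensitive to this input. A reader might infer that 0.55 is a miscalculation. It is not: it reproduces and is a legitimate bound for its own model. What stands is that it is never tied to a planned test.

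**The two power calculations do not conflict.** A reader might set "our required sample size is 106 prisoners" for an effect of 0.5 against a worst case of 0.55 with 400 and see a contradiction. The GPower paragraph says that it ignores the multiple sites, so the assumptions differ and are declared.

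**The target population is not settled.** All four county prisons are included, but the Project summary speaks of prisoners in Norway, and Geographic region argues that Rogaland resembles other counties. If wider inference is intended, 0.55 is the relevant kind of figure and the gap lies in the analysis model. This objection stands, and it is why 0.55 should be labelled, not removed.

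**The 0.15 to 0.18 is an approximation.** It assumes a linear model, equal prisons and 400 analysed. The plan uses ordinal logistic regression, adds dummies for the person who delivered the conversation (coding for controls unstated), expects fairly high attrition, and notes that one prison has only 18 rooms. All of this stands and limits the replacement figures.

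**A threefold gain in sensitivity must not be read across to T2.** The ratio 0.547/0.178 is about 3, but only for the adjusted regression at 400. For Mann-Whitney at 400 it is 0.547/0.287, about 1.9, and with 200 analysed that test detects only about 0.41.

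**No design decision hangs on 0.55.** Recruitment is set by capacity. The consequence is confined to interpretation.

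**Conclusion.** The point holds in a limited form. The published range joins a fixed-effects figure to a random-prison-effects figure, and only the lower end corresponds, approximately, to a planned analysis. For the planned tests at 400 analysed, the detectable effect is about 0.15 to 0.18 for the prison-dummy, baseline-adjusted regression and about 0.29 for Mann-Whitney; at an assumed 200, about 0.21 to 0.25 and about 0.41.

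These values rest on the plan's B and R², two-sided 0.05, power 0.8, equal prisons and, for the regression, a linear approximation that is slightly optimistic for the seven-level score. The validity of the trial is not in question. The correction should be made because the plan relies on this section to interpret a null at T2.

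**What to change.** In Power calculations, give one detectable effect per planned test, stating two-sided 0.05 and power 0.8: about 0.15 to 0.18 for the regression (linear approximation, equal prisons, 400 analysed; somewhat larger for the ordinal score) and about 0.29 for Mann-Whitney at 400. Add values for the smaller numbers expected at T1 and T2, such as those for 200 above. Note that 106 and 320 match a one-sided test, so that 0.286 at 320 and 0.29 at 400 can be read side by side.

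Keep 0.55 only with the label that it applies to generalising to prisons beyond these four. State that the prison-dummy regressions estimate the average effect in these four prisons. If wider inference is intended, the analysis must model treatment-by-prison variation. Report the effect by prison descriptively, since the plan identifies this variation as its most influential unknown.

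The cost is redrafting and one descriptive table, with no new data or participants. The downside is a claim explicitly limited to the four prisons unless the analysis model changes.
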